10.6 Interim Analysis

Interim data analysis of the primary efficacy and safety endpoints is planned after 200 subjects have been enrolled. Additional interim analyses will be conducted after every 50 subjects are enrolled. The interim analyses will include imputing the 180 day mRS score for subjects who do not have a 180 day score. Based on the predictive probability that the study would be a success the study may be stopped early for futility or enrollment may be stopped based on expected success. The specific details of the planned analyses are described completely in the adaptive design report.

10.7 Statistical Evaluation of Primary Endpoint

The primary endpoint is the Day 180 global disability assessed via the ordinal modified Rankin score (mRS).

The null hypothesis is that the cumulative odds ratio for mRS at 180 days in the MIS group compared to MM group is less than or equal to 1. The alternative hypothesis is that the cumulative odds ratio for mRS at 180 days is greater than 1. Formally, the null and alternative hypotheses to be tested are as follows:

$$H_0: OR \leq 1$$

$$H_A: OR > 1,$$

where OR is the cumulative odds ratio for the mRS at the 180 day follow-up visit, with higher values indicating better outcomes in the MIS treatment group.

Statistical analysis of the primary endpoint will be conducted using a logistic regression analysis of the 180 day mRS scores. The primary efficacy endpoint is met if the overall treatment effect is positive at a one-sided alpha of 0.02. The odds ratio and corresponding 95% confidence interval will be estimated from the proportional odds model. The primary analysis will be unadjusted. A secondary analysis model will include the minimization variables of Hemphill Score and hemorrhage location.

The mRS scores of 5 and 6 will be combined into a single group for the purposes of endpoint evaluation. Subjects deceased during study follow-up will be scored as mRS 6.

10.8 Statistical Analysis of Primary Safety Outcome

With the date of randomization set at day 0, any death occurring on or before Day 30 will be included as a death.

10.9 Secondary Statistical Analysis

The secondary endpoints of Day 180 and Day 365 average improvement in global disability will be assessed via the weighted modified Rankin score (mRS) and will be analyzed using a generalized linear model. The mRS scores will be weighted as

the following: 1.0 for mRS level 0; 0.91 for mRS level 1; 0.76 for mRS level 2; 0.65 for mRS level 3; 0.33 for mRS level 4; 0 for mRS level 5; and 0 for mRS level 6.⁶⁵ Statistical analysis of the dichotomized Rankin outcome scores of 0 to 2 and 0 to 3 will be conducted with a logistic regression model. Group differences will be analyzed for the following: SIS-ADL, SIS-mobility, EQ-5D-5L, length of stay, length of procedure. Other pre-specified analyses will be performed as outlined in the statistical plan.

10.10 Baseline Characteristics

Baseline data will be analyzed to assess the comparability of treatment groups. Baseline data including, but not limited to demographics, clinical characteristics, and baseline ICH characteristics will be summarized using descriptive statistics. Statistical testing will be performed as appropriate.

10.11 Pooling Across Centers

Analyses will be presented by treatment group using data pooled across sites. The site analysis will be conducted using an ordinal logistic regression with terms of treatment group and treatment-by-site interaction. This analysis will be performed on the intent-to-treat population. The primary statistical inference is the treatment-by-site interaction, which is tested at the significance level of 0.15. When the treatment-by-site interaction is statistically significant ($p \leq 0.15$), the treatment group differences will be evaluated within each site. Adjusted analysis on the primary outcome using key baseline variables will be used for the site analyses for consistency with the overall study result. If the odds ratio of the treatment effect is found to vary by site, then a random-effects model analysis will be performed to assess whether there was significant variance in the primary endpoint according to study site.

10.12 Health Economics Information

The study site will complete CRFs containing healthcare utilization information (e.g., ICU days). This information may be used for analyses to compare overall healthcare costs and resource utilization between MIS and MM.

10.13 Final Report

A final report will be completed, even if the study is prematurely terminated. At the conclusion of the study, a multi-center abstract reporting the results will be prepared and may be presented at a major meeting(s). A multi-center publication may also be prepared for publication in a reputable scientific journal. The publication of results from any single center experience within the study is not allowed until the aggregate study results have been published, unless there is written consent from the Sponsor.

11. Study Committees and Core Labs

11.1 Steering Committee/Scientific Advisory Board

The Steering Committee (SC) and/or Scientific Advisory Board (SAB) will be comprised of physicians with subject matter expertise. The SC/SAB will be advisors to the Sponsor regarding study planning, execution and data presentation, progress of enrollment, subject safety and consideration of new information. Daily study management is the responsibility of the Penumbra. The SC/SAB will oversee dissemination of study results through appropriate scientific sessions and publications. The SC/SAB may recommend additional investigators, based on enrollment and adherence to the protocol, to participate on a Publication Committee. The Publication Committee will participate in the review and approval of all requests for data analysis, abstract and manuscript preparation and submission.

11.2 Safety Monitoring Committees

11.2.1 Data Safety Monitoring Board (DSMB)

A DSMB will be comprised of members not participating in the study and will include neurovascular specialist physicians and a statistician. The DSMB will exercise review of the overall safety of the study and make recommendations to adjustments in the study protocol, should any be considered necessary for safety or other related reasons. Additional details will be specified in the DSMB charter.

11.2.2 Clinical Events Committee (CEC)

The Clinical Events Committee (CEC) is made up of independent medical doctors who are not participants in the study. The CEC is charged with the development of specific criteria used for the categorization of clinical events and clinical endpoints in the study which are based on the protocol.

At the onset of the study, the CEC will establish explicit rules outlining the minimum amount of data required, and the algorithm followed in order to classify a clinical event. While the CEC review of adverse events specific to the interventional procedure will unblind the members, all members of the CEC will be blinded to the overall primary results of the study.

The CEC will review and adjudicate appropriate clinical events, mainly related to the device and to the study endpoints. The CEC will also review and rule on all deaths that occur throughout the study. The safety process flow and a web-based electronic database will be provided to CEC members for case review and adjudication. The designated Penumbra staff who are responsible for reviewing safety data on an ongoing basis will coordinate collection of information for the event dossier.

11.3 Imaging Core Lab

The independent imaging core lab will review images from the procedure to determine, at a minimum, hematoma volume. An Imaging core lab charter will provide procedure for core lab review. Penumbra, or designee, is responsible for tracking images received, basic quality review and forwarding applicable results to the CEC.

12. Study Administration

12.1 Clinical Trial Termination/Withdrawal

Subjects may be terminated or withdrawn from the study for the following reasons:

- Voluntary withdrawal of consent — Meaning that a subject voluntarily chooses not to participate further in the study. All data collected up to the date of withdrawal of consent will be maintained in the study database. Withdrawn subjects will not have any additional follow-up and will not be replaced.
- Lost to follow-up — A subject will not be considered lost-to-follow-up until contact is not achieved at the 365 day visit. At a minimum, the effort to obtain follow-up information will include three attempts to make contact via telephone or e-mail and if unsuccessful, a letter from the Investigator sent via courier or other traceable method will be sent to the subject's last known address. These efforts to obtain follow-up will be recorded in the subject's study files and the case report forms.
- Subjects may also be withdrawn at the investigator's discretion if within their best interest. A subject's participation in the clinical study will be terminated if the investigator believes that this is in the subject's best medical interest or if the subject no longer complies with the clinical study requirements.

The Sponsor may temporarily suspend or prematurely terminate the study at any time for the following reasons:

- Suspicion of risk to subjects
- If no positive IRB/EC decision is obtained or if the judgement of the IRB/EC is revoked
- If the applicable regulatory body has made an irrevocable objection
- If it transpires that continuation of study cannot serve any scientific purpose, and this is confirmed by the IRB/EC
- Business reasons (e.g., Sponsor has been declared insolvent, or if a petition has been filed for liquidation)

The Sponsor will document reasons for study suspension or premature termination and notify the PIs. The Sponsor will ensure that the IRB/ECs and regulatory authorities (if required) are notified in a timely manner.

The Sponsor will continue to provide resources to fulfill the obligations from the study protocol and existing agreements for following up the subjects enrolled in the study.

The Principal Investigators will promptly inform the enrolled subjects at his/her site, if appropriate.

If the Sponsor temporarily suspends the study and wishes to resume it, the Sponsor will inform the PIs, IRB/ECs and (if appropriate) regulatory authorities. The Sponsor will provide a rationale for resuming the study. IRB/ECs must provide written approval before the study is resumed.

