4.3 Method of Randomization

Randomization takes place centrally through a commercially available Interactive Web Response System (IWRS). Randomization will occur in a 2:1 ratio to either MIS or MM. The treatment allocation will be balanced by Hemphill Score (0 – 2, 3 – 4) and hemorrhage location (primarily lobar, primarily deep). Once a patient is determined to meet all study eligibility criteria, the Investigator (or authorized team member) obtains the treatment assignment for that subject. Crossover is not permitted after randomization. Once a subject is randomized, the subject is

considered enrolled in the study and that subject must be followed through to the end of study or to subject's termination of consent.

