10.5.2 Intent to Treat Sample

As the primary analysis, all efficacy and safety outcome measures will be analyzed under the intent-to-treat (ITT) principle. Under this principle, the evaluable sample includes all subjects who are randomized. Each subject will be analyzed according to the treatment group to which they were randomly assigned at the time of randomization. This population is the primary population for all efficacy parameters.

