12.3 Missing Visits

Any study subject who does not attend a scheduled follow-up visit should be contacted by site personnel to determine the reason for the missed appointment(s).

If the missed visit was due to a serious adverse event, (e.g., re-hospitalization) an AE CRF must be completed and any reporting requirements met. Every effort should be made in order to bring subject in to scheduled follow-up visits.

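### Protocol 12.1 ends participation for non-compliance, while 4.3 requires follow-up of every randomized subject until study end or termination of consent; the two must be reconciled so that Day 180 outcomes are not lost by an unblinded decision

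*Protocol*

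**What the plan says.** Protocol 12.1 (Clinical Trial Termination/Withdrawal), third bullet: "A subject's participation in the clinical study will be terminated if the investigator believes that this is in the subject's best medical interest", and the sentence goes on, "or if the subject no longer complies with the clinical study requirements". The verb is mandatory, and non-compliance is a separate trigger from medical interest.

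Protocol 4.3 (Method of Randomization), on a subject once randomized: "that subject must be followed through to the end of study or to subject's termination of consent". Termination of consent is the only exception.

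Other provisions bear on the point:

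- Protocol 12.1, consent-withdrawal bullet: "Withdrawn subjects will not have any additional follow-up and will not be replaced".
- Protocol 12.1, lost-to-follow-up bullet: "A subject will not be considered lost-to-follow-up until contact is not achieved at the 365 day visit".
- Protocol 12.3 (Missing Visits): "Every effort should be made in order to bring subject in to scheduled follow-up visits".
- Protocol 10.3 aims to minimize missing data, above all at Day 180.
- Protocol 10.5.2 defines the primary analysis set: "Under this principle, the evaluable sample includes all subjects who are randomized".
- Protocol 4.4: the sponsor's clinical team, investigator, site staff and subject know the assigned arm. Only the assessor of the 180-day mRS is blinded.
- SAP 13: a missing Day 180 mRS is replaced by one median value from a Bayesian longitudinal model, using the last available score (Day 30 or Day 90 are named). Complete-case, all-missing-as-5/6, worst-case and multiple-imputation analyses are planned as sensitivity analyses.

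**The concern.** Both rules are worded as obligations, and they give opposite instructions for a subject who stops complying but has not withdrawn consent. The study intervention is a single procedure within 72 hours of the bleed, so after that there is no continuing study treatment to stop. Ending participation then mainly ends the collection of outcomes.

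The decision lies with an investigator who knows the arm. If terminations are related to how the subject is doing, and differ between arms, the intent-to-treat comparison of the Day 180 mRS rests on imputed values for a selected group, and vital status after termination is lost as well. The blinded 180-day assessment gives no protection, because the blinded assessor does not decide who reaches it.

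**Working it through.** **1. The passages side by side**

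| Situation after randomization, consent not withdrawn | 4.3 | 12.1, third bullet | Other text |
|---|---|---|---|
| Subject misses a visit | Keep following | Not addressed as such | 12.3: make contact, try to bring the subject in. 12.1: not lost to follow-up before Day 365 |
| Subject is judged non-compliant | Keep following | End participation | None reconciles the two |
| Outcomes after termination for non-compliance | Still due | Implied to cease | None preserves them; none expressly forbids them |

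The conflict is confined to the second and third rows, and it is real there.

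**2. Reproducing the plan's power**

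Inputs: N = 500, 2:1 allocation, cumulative OR 1.7, MM distribution 3/10/7/7/14/59% with mRS 5 and 6 merged (Protocol 10.1, Table 3), one-sided 0.02 at the final analysis (Protocol 10.7).

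Shifting the MM row by OR 1.7 gives 5.0/15.3/9.6/8.8/15.6/45.8% for MIS. The 2:1 weighted mean proportions are 4.3/13.5/8.7/8.2/15.0/50.2%, and the sum of their cubes is 0.134.

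Whitehead information: V = N × r/(1+r)² × (1 − Σp̄³)/3 = 500 × 2/9 × 0.866/3 = 32.1, so √V = 5.66.

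Power = Φ(ln 1.7 × √V − 2.054) = Φ(3.005 − 2.054) = 82.9%.

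A 200,000-run simulation of the tie-corrected Wilcoxon test gives 81.6%. Both are within two points of the stated 81%. The full adaptive operating characteristics cannot be rebuilt, because the adaptive design report is not among the documents.

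**3. Equal, uninformative loss (rates assumed)**

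Same simulation, one-sided 0.02, full-follow-up power 81.6%:

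| Lost in each arm | Complete-case power | Missing scored 5/6 |
|---|---|---|
| 2% | 80.8% | 80.2% |
| 5% | 79.6% | 78.0% |
| 10% | 77.3% | 73.6% |

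Complete-case, the cost is 0.8, 2.0 and 4.3 points.

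**4. Unequal, outcome-related loss (rates and selection assumed)**

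No treatment effect, N = 500, complete-case, nominal one-sided 0.02:

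| Lost MM / MIS | Lost from mRS 0-3 | Lost from mRS 4-6 |
|---|---|---|
| 2% / 2% | 0.019 | 0.019 |
| 5% / 5% | 0.019 | 0.019 |
| 5% / 2% | 0.056 | 0.013 |
| 2% / 5% | 0.006 | 0.029 |
| 5% / 0% | 0.097 | 0.010 |

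With 333 MIS and 167 MM subjects, the 5%/2% row means about 8 MM and 7 MIS subjects. The error can move either way, depending on who is lost. Equal loss leaves it unchanged. These are complete-case figures. The primary analysis imputes from the last score, which recovers part of the information but cannot correct selection that the earlier score does not explain. A subject terminated before Day 30 has neither of the scores that SAP 13 names as a source.

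**The case against.** Several stronger readings are tempting, and the documents do not support them.

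- *The protocol forbids follow-up after non-compliance.* The sentence that rules out further follow-up stands in the consent-withdrawal bullet. The investigator bullet shares the word withdrawn but does not repeat the rule. For non-compliance the loss is an inference. The list in 12.1 also opens permissively, although the sentence at issue is mandatory.
- *One missed visit means permanent loss.* Section 12.3, the lost-to-follow-up rule and its required contact attempts say otherwise, and Protocol 7.6.2 treats missing data and out-of-window visits as deviations to document.
- *The intent-to-treat definition requires follow-up.* It says who is analyzed, and in which arm. Only 4.3 carries the conflict.
- *Non-compliance can only mean missed visits.* A subject could refuse the assigned procedure or join another interventional trial.
- *A few losses would overturn the primary result.* Under the SAP's worst case (missing MIS scored 5/6, missing MM scored 0), expected counts of 333/167 at OR 1.7 give one-sided p of 0.0017, 0.011, 0.024 and 0.090 at 0, 2, 3 and 5% missing per arm. That is the most extreme planned sensitivity analysis and has no success threshold. Complete-case, p stays at about 0.002 throughout.

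It is also fair to say that nothing in the documents shows that control subjects would be terminated more often, and that the sensitivity analyses would reveal fragility. All of this limits the size of the point. None of it tells a site which of the two rules to follow.

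**Conclusion.** The contradiction between 4.3 and 12.1 stands and is unresolved. The safe conclusion is that 12.1 permits, and on its wording directs, an avoidable and unblinded loss of Day 180 mRS and later vital status.

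Its size is unknown, because no termination rate is given. If loss is equal and uninformative, the harm is small: about 1-4 points of complete-case power at an assumed 2-10%. If it is unequal and outcome-related, the error rate can shift materially (0.006 to 0.097 in the assumed cases against a nominal 0.02). Imputation and sensitivity analyses reduce this exposure without removing it. A reader should not infer that the stated sample size or power is wrong: the 81% reproduces. The point should be addressed because prevention is cheap and bias of this kind cannot be repaired at analysis.

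**What to change.** In Protocol 12.1, delete non-compliance as a ground for ending participation. Add that, unless consent is withdrawn, subjects who stop attending or deviate from the protocol remain in follow-up. Their Day 180 mRS is sought through the planned in-person blinded assessment, and vital status to Day 365 is collected by telephone or from records.

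The telephone or records route should not extend to the Day 180 mRS. Protocol 6.10.1 requires that assessment in person, and 4.4 requires a blinded assessor and a scripted interview.

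The medical-interest ground in the same sentence is a clinical matter on which I take no position. Since 4.3 does not list it either, the reconciled text should say what is still collected in that case.

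The cost is a protocol wording change and some extra contact effort within the existing visit schedule. Sample size and the primary analysis are unaffected.

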12.2 Stopping the Trial Based on Interim Safety Data

The DSMB will receive periodic safety reports of all reported AEs and SAEs. In addition, the following specific endpoints will be assessed by the medical monitor and presented:

- Death (all cause) within 30 days of enrollment
- Death within 7 days of enrollment: Immediate periprocedural death
- Symptomatic Re-Hemorrhage or New Hemorrhagic Event: Any new intracranial hemorrhage or increase in size of pre-existing hemorrhage (IPH, IVH or extra-axial bleed) within 30 days associated with an increase of 4 or more points on the NIHSS or GCS decrease > 2 persisting for at least 24 hours, requiring emergency surgical decompression or resulting in death
- Symptomatic Evolution of Perihematomal Edema: Edema with increased mass effect or uncontrolled ICPs within 30 days requiring emergency surgical decompression NOT related to new or increased hemorrhage (i.e., edema related) associated with an increase of 4 or more points on the NIHSS or GCS decrease > 2 persisting for at least 24 hours, requiring emergency surgical decompression or resulting in death
- Symptomatic Ischemic Stroke: A new ischemic stroke (ipsilateral, contralateral; contiguous with bleed/operative site or remote; cortical, subcortical or perforator distribution) within 30 days associated with an increase of 4 or more points on the NIHSS or GCS decrease > 2 persisting for at least 24 hours, requiring emergency surgical decompression or resulting in death
- Surgical complications related to MIS: Surgical site infection, brain abscess or confirmed meningitis, or documented complication(s) deemed specifically related to the procedural anesthetic (medication, access or intubation related) within 30 days

Additional details regarding the DSMB structure and stopping rules will be included in the DSMB charter.

12.3 Missing Visits

Any study subject who does not attend a scheduled follow-up visit should be contacted by site personnel to determine the reason for the missed appointment(s).

If the missed visit was due to a serious adverse event, (e.g., re-hospitalization) an AE CRF must be completed and any reporting requirements met. Every effort should be made in order to bring subject in to scheduled follow-up visits.

12.4 Protocol Adherence and Amendments

Prior to beginning the study, the Principal Investigator must sign the protocol signature page documenting his/her agreement to conduct the study in accordance with this protocol. An Investigator must not make any changes or deviate from this protocol, except to protect the life and physical well-being of a subject in an emergency. Each deviation from the protocol must be documented with the date and reported to Penumbra as soon as possible, and to the IRB/EC per local guidelines and government regulations.

The protocol must be followed exactly. It can be altered only by written amendments made by Penumbra. Following appropriate approval by Penumbra the amended protocol will be submitted to the required regulatory agencies before being distributed to all participating sites. Each site must obtain IRB/EC approval before implementing the revised protocol.

